10.4 Safety

The safety sample will be used for the analysis of the safety and tolerability data.

AEs are considered treatment emergent (TE) if they start or worsen at or after the first administration of study drug and before or on the day of last administration of study drug plus a gap period of 1 day.

AEs will be reported on a per-subject basis, i.e. counting subjects rather than events. This means that if a subject suffers the same AEs repeatedly during the applicable study period, the event will be counted only once for that period. Repeated events per subject will be summarized according to the following rule: if a subject suffered the same AE more than once, the event will be assigned the worst severity, the closest relationship to the study drug and the earliest starting date. Only treatment emergent AEs will be reported. In the listings, however, all occurrences of the AEs will be presented.

For each unique treatment, treatment emergent AEs will be summarized per primary SOC, per HLT by primary SOC and per PT by HLT and primary SOC. Severity and drug-event relationship of treatment emergent AEs are summarized separately. Non-TEAEs will be listed.

Vitals signs, including changes from baseline will be summarized. A frequency table will be presented for markedly abnormal values.

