4.3 Safety analysis

The Safety Sample will be used for the analysis of the safety and tolerability data.

Descriptive statistics for all safety and tolerability data will be presented by treatment arm and by stratification level (Age Category).

AEs are considered treatment emergent (TE) if they start or worsen at or after the first administration of study drug and before or on the day of last administration of study drug plus a gap period of 1 day (24 hours).

AEs will be reported on a per-subject basis, i.e. counting subjects rather than events. This means that if a subject suffers the same AEs repeatedly during the applicable study period, the event will be counted only once for that period. Repeated events per subject will be summarized according to the following rule: if a subject suffered the same AE more than once, the event will be assigned the worst severity, the closest relationship to the study drug and the earliest starting date. Only treatment emergent AEs will be reported. In the listings, however, all occurrences of the AEs will be presented.

For each unique treatment, treatment emergent AEs will be summarized per primary SOC, per HLT by primary SOC and per PT by HLT and primary SOC. Severity and drug-event relationship of treatment emergent AEs are summarized separately. Non-TEAEs will be listed.

Vitals signs: Height (m), Weight (kg), Systolic Blood Pressure (mmHg), Diastolic Blood Pressure (mmHg), Pulse (bpm), including changes from baseline will be summarized. A frequency table will be presented for markedly abnormal values (presented in the table categories includes "to high", "to low" and "normal" levels based on normal ranges).

Temperature data will be presented in appropriate listing only.

RACE3003 clinical study was conducted with the involvement of local laboratories, thus local normal ranges have been used in each particular site (the ranges are presented below). Additional footnote ("Created *
* based on site specific ranges.") will be presented for appropriate tables and listings in the statistical analysis report.

Normal Heart Rate by Age (beats/minute)											
Site Age	1	2	3	4	5	6	7	8	9		
1-12 month	100-140	100-190	100-190	100-160	100-190	100-190	110-170	100-190	100-190		
1-3 years	98-120	98-140	95-110	98-140	98-140	98-140	100-130	98-140	98-140		
3-6 years	80-105	80-120	80-120	80-120	80-120	80-120	85-115	80-120	80-120		
6-9 years	75-90	75-118	75-110	75-118	75-118	75-118	75-105	75-118	75-118		

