9-12 years	70-90	60-100	60-100	60-100	60-100	60-100	70-90	60-100	60-100		
12-18 years	70-90	60-100	60-100	60-100	60-100	60-100	70-90	60-100	60-100		

Normal Systolic Blood Pressure by Age (mm Hg)											
Site Age	1	2	3	4	5	6	7	8	9		
1-12 month	80-112	90-112	85-105	90-112	90-112	90-112	75-80	90-112	90-112		
1-3 years	90-112	100-112	85-110	100-112	100-112	100-112	80-85	100-112	100-112		
3-6 years	100-116	100-116	85-115	100-116	100-116	100-116	90-95	100-116	100-116		
6-9 years	100-122	100-122	95-120	100-122	100-122	100-122	95-105	100-122	100-122		
9-12 years	100-126	110-126	110-125	110-126	110-126	110-126	105-115	110-126	110-126		

Normal Systolic Blood Pressure by Age (mm Hg)											
Site Age	Site 1 2 3 4 5 6 7 8 9										
12-18 years	110-120	110-136	110-130	110-136	110-136	110-136	110-120	110-136	110-136		

Normal Diastolic Blood Pressure by Age (mm Hg)											
Site Age	1	2	3	4	5	6	7	8	9		
1-12 month	50-74	50-74	45-60	50-74	50-74	50-74	50-74	50-74	50-74		
1-3 years	60-74	60-74	50-60	60-74	60-74	60-74	50-55	60-74	60-74		
3-6 years	60-76	60-76	55-60	60-76	60-76	60-76	50-60	60-76	60-76		
6-9 years	60-78	60-78	55-70	60-78	60-78	60-78	65-70	60-78	60-78		
9-12 years	70-82	60-82	55-70	70-82	70-82	70-82	70-75	70-82	70-82		
12-18 years	70-86	60-86	55-70	70-86	70-86	70-86	70-80	70-86	70-86		

Temperature (C)										
Site Age	1	2	3	4	5	6	7	8	9	
Axillary	36,1-	35,9-	36,3-	36,3-	36,3-	36,3-	36,3-	36,3-	36,3-	
	36,9	36,9	36,9	36,9	37,0	36,9	36,9	36,9	36,9	
Oral	36,8-	36,2-	36,8-	36,8-	36,8-	36,8-	36,8-	36,8-	36,8-	
	37,3	37,3	37,3	37,3	37,3	37,3	37,3	37,3	37,3	
Rectal	37,1-	36,9-	37,3-	37,3-	37,3-	37,3-	37,3-	37,3-	37,3-	
	37,9	37,9	37,7	37,7	38,0	37,7	37,7	37,7	37,7	
Tympanic	36,1-	36,5-	37,3-	37,3-	37,3-	37,3-	37,3-	37,3-	37,3-	
membrane	36,9	37,5	37,7	37,7	37,7	37,7	37,7	37,7	37,7	
Skin / Temporary artery	36,1- 36,9	36,3- 36,9								

Physical Examination will be summarized by subgroup (toilet trained, not toilet trained and overall).

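### Site-specific normal ranges give the abnormal vital-sign counts no consistent meaning; in four parameter-by-age cells the same reading is too high at site 7 and too low at six or seven other sites

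*SAP*

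**What the plan says.** Protocol 10.4 promises, for vital signs, that "A frequency table will be presented for markedly abnormal values". SAP 4.3 repeats this and adds how values are classed: "presented in the table categories includes 'to high', 'to low' and 'normal' levels based on normal ranges". It refers to the involvement of local laboratories, says that "local normal ranges have been used in each particular site", and prints ranges for nine sites by age band for heart rate, systolic pressure and diastolic pressure.

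The only handling of differences between sites is a footnote stating that the output is "based on site specific ranges". The outputs concerned are table 10.1.3.2.2 and listing 12.2.8.8, both titled as markedly abnormal vital signs. SAP 4.3 gives no common reference, no separate threshold for a marked abnormality and no supporting version of the table. Temperature is assigned to a listing only.

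**The concern.** Local reference ranges make sense for laboratory assays, whose methods and units differ between laboratories. Blood pressure and pulse are physical measurements, so the reason given does not explain why a child's reading should be judged differently by site.

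Where site ranges differ, pooling the flags adds readings of one value into different columns. Where two ranges do not overlap at all, one value is counted as low for one child and high for another. Vital signs are one of the three safety measures named in the protocol's safety objective, and this is the table a reader would scan for a signal. Each cell count would then combine the child's reading with the local table used to judge it.

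**Working it through.** **Inputs.** All ranges come from the tables in SAP 4.3. There are three parameters (heart rate, systolic, diastolic) and six age bands, so 3 × 6 = 18 cells, each with nine site ranges. The systolic ranges that matter most are these:

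- In the band from 1 to 3 years, the row for sites 1 to 9 in order reads "90-112 100-112 85-110 100-112 100-112 100-112 80-85 100-112 100-112".
- In the first year of life, site 7 has 75-80, site 1 has 80-112, site 3 has 85-105 and the other six sites have 90-112.
- In the band from 3 to 6 years, site 7 has 90-95, site 3 has 85-115 and the other seven sites have 100-116.

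For diastolic at 1-3 years, site 7 has 50-55, site 3 has 50-60 and the other seven sites have 60-74.

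**Rule.** For a site with range L to U, a reading x is too low if x < L, too high if x > U, and normal otherwise. Counting the end values as normal is my assumption. A reading is reversed between site 7 and another site when it lies above site 7's upper limit and below the other site's lower limit. In whole mmHg the reversed readings run from (site 7's U + 1) to (the other site's L − 1).

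**Reversals.**

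| Cell | Site 7 | Highest lower limit elsewhere | Reversed readings | Too low at |
|---|---|---|---|---|
| Systolic, 1-12 months | 75-80 | 90 (sites 2, 4, 5, 6, 8, 9) | 81-89 | 7 sites for 81-84 (site 3 added, L = 85); 6 sites for 85-89 |
| Systolic, 1-3 years | 80-85 | 100 (sites 2, 4, 5, 6, 8, 9) | 86-99 | 7 sites for 86-89 (site 1 added, L = 90); 6 sites for 90-99 |
| Systolic, 3-6 years | 90-95 | 100 (all but 3 and 7) | 96-99 | 7 sites |
| Diastolic, 1-3 years | 50-55 | 60 (all but 3 and 7) | 56-59 | 7 sites |

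Single readings at 1-3 years:

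- Systolic 88: low at sites 1, 2, 4, 5, 6, 8, 9 (seven); normal at site 3; high at site 7.
- Systolic 95: low at sites 2, 4, 5, 6, 8, 9 (six); normal at sites 1 and 3; high at site 7.
- Diastolic 57: low at seven sites; normal at site 3; high at site 7.

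In each of the three systolic cells, site 7's range fails to overlap that of seven of the eight other sites.

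**The other cells.** The same test over every whole-number reading finds no low/high reversal in the remaining 14 cells: none for heart rate, none for systolic from 6 years, and none for diastolic outside 1-3 years. Disagreement between normal and abnormal occurs in all 18. The number of whole-number readings affected runs from 16 (systolic, 12-18 years: 121-136) to 60 (heart rate, 1-12 months: 100-109 and 141-190).

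**Effect on a change.** Take a child aged 1-3 years whose systolic pressure falls from 95 to 83. The flags go from high to normal at site 7, from normal to low at sites 1 and 3, and from low to low at the other six. The same fall is recorded in three different ways.

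**The case against.** The strongest reply is that little depends on this table. It is descriptive and no test is planned on it. The SAP prints every range and footnotes the method. Actual values and changes from baseline are summarised separately (table 10.1.3.2.1), and all vital signs are listed (12.2.8.9), so anyone can reclassify. All of that stands. It limits the consequence but does not repair the rule for table 10.1.3.2.2.

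Site 7's figures may also be a transcription fault. At 1-12 months its systolic range is 75-80 beside a diastolic range of 50-74, and its diastolic range then narrows to 50-55 at 1-3 years. The documents do not settle this. An error there would explain every low/high reversal, but not the normal/abnormal disagreements among the other sites.

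The SAP's reference list cites a sponsor standard module, which I have not seen and which might define a marked abnormality. SAP 4.3 nevertheless bases the categories on the normal ranges, and SAP 6.2 adds nothing to the standard tables.

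A reader might infer that the table shows site rather than drug safety, or that it will produce a false difference between arms. The documents do not support that. Both arms at a site are judged by the same ranges, so with randomisation no systematic tilt towards one arm is expected. Enrolment by site is not given. If 124 subjects were spread evenly (an assumption), site 7 would hold 124 / 9 ≈ 14, of whom only those under 6 years could fall in a reversal cell. Protocol 7.4 does not mention site in the randomisation, but it is brief and partly redacted, so balance within site can be neither assumed nor ruled out.

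**Conclusion.** The point holds within limits. Followed as written, SAP 4.3 puts identical readings into different columns of table 10.1.3.2.2. Disagreement on normal versus abnormal affects 18 of 18 cells; outright low/high reversal affects 4 of 18 and always involves site 7. It would be wrong to conclude that vital signs in general are low at one site and high at another.

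The pooled counts partly reflect site. The risk between arms is noise, or a masked difference, through chance imbalance of sites. Its size cannot be estimated without enrolment by site and age. Equal numbers by arm within site would remove that imbalance, but the columns would still mix unlike classifications. The affected ages are in the trial: entry starts at 3 months, and at least 20 subjects are planned in the group under 24 months. Efficacy and the continuous vital-sign summaries are untouched. The correction is worth making before lock, but it does not threaten the trial's main conclusion.

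**What to change.** 1. Check site 7's printed ranges against the source supplied by the site, and reconcile any discrepancy in the SAP.
2. Produce table 10.1.3.2.2 and listing 12.2.8.8 with one common age-specific reference table for all nine sites. The trial's medical expert should choose it, and it should be fixed before database lock without reference to results by arm. Six sites already share identical systolic ranges in every band, which shows that a common table is workable, not which limits are right.
3. Keep the site-specific flags in a listing only.
4. Either retitle the table as values outside the reference range, or state a separate criterion for a markedly abnormal value. A common range alone does not justify the present title.

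The cost is a change of SAP wording and one lookup table, with no new data. There are two drawbacks. Some flags will differ from those the sites saw. The reference would also be chosen late: SAP 4.3 already describes the study in the past tense, and the trial is open-label. That is why the choice must be documented as made without sight of results by arm.

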4.4 Interim Analysis

No interim analysis is planned.

4.5 Data Safety Monitoring Board

Not applicable.

4.6 Safety Management Team

Not applicable.

5. DESCRIPTION OF NON-STANDARD DATA COLLECTED AND DERIVED VARIABLES

5.1 Other Non-Standard Baseline Characteristics

Other baseline characteristic collected in the study is Main Diagnosis. The main Main Diagnosis data will be tabulated using descriptive statistics and listed.

5.2 Non-Standard Disease History

Not applicable.

5.3 Efficacy data

The efficacy data collected are:

- Information about diarrheal/watery stool/stool from Subjects Diary (domain SS);
- Global physician assessment at the end of treatment (domain QS).

5.4 Non-standard Safety Data

The following non-standard safety data are collected: Physical Examination (PE domain).

5.5.2 Exposure

Exposure analysis will be provided using EC domain. Descriptive statistics tables will be presented for:

- Mean duration of treatment¹ (in hours) by weight subgroups (less than 9 kg, from 9 kg to < 13 kg, from 13 kg to 27 kg, from more than 27 kg to 60 kg, 60 kg or higher) and overall;
- Mean duration of treatment (in hours) by age subgroup and overall;
- Cumulative dose divided by weight (mg/kg).

¹ The duration of treatment will be assumed as 1 hour in case of single dose administration.

6. FURTHER SPECIFICATIONS TO THE STANDARD ANALYSES IN MODULE 2

6.1 Trial Design [2]

6.1.1 Trial Periods

The combination of trial arms and trial periods for the current trial is presented in the following diagram:

		Screening Period	Treatment Period	Follow-up Periods	
Trial Arm A	Subgroup	Screen	Racecadotril + ORS	Follow-up	
(RACE+ORS)	11				
	Subgroup B	Screen	Racecadotril + ORS	Follow-up	
	Subgroup C	Screen	Racecadotril + ORS	Follow-up	
Trial Arm B (ORS)	Subgroup A	Screen	ORS	Follow-up	
	Subgroup B	Screen	ORS	Follow-up	
	Subgroup C	Screen	ORS	Follow-up	

Subgroups are defined by age categories:

- Subgroup A (from 3 to < 24 month)
- Subgroup B (from >= 2 to <12 years)
- Subgroup C (12 to < 18 years),

6.1.2 Trial Elements

The start time of each intervention will be expressed relative to the first administration of investigational study drug closest to that intervention.

Trial Element	Description of Element	Rule for Start of Element	Rule for End of Element	Planned Duration of Element
Screen	Screening period	Date of Informed Consent	First dose of study treatment	
Racecadotril + ORS	Treatment period	First dose of Racecadotril + ORS	Last dose of Racecadotril + ORS	5 days or less
ORS	Treatment period	First dose of ORS	Last dose of ORS	5 days or less
Follow-up	Safety Follow-Up period	Last dose of study treatment	Investigator's phone call 5-7 days after end of treatment visit	5-7 days

The Trial Elements are presented in the following diagram:

6.1.3 Trial Arms

The trial arms for this study are made up of the following trial elements:

	Elements						
Trial Arm	Screen	Racecadotril + ORS	ORS	Follow-up			
А	Y	Y	N	Y			
В	Y	Ν	Y	Y			

6.1.4 Visits and related definitions

Tests and examinations that were scheduled in the protocol will be related to the general time axis of the trial by relating the visit date on which a test or examination is performed to the start date of the trial element that describes the first administration of investigational study drug closest in time to the visit date of that test or examination (Reference Start Date/ Time).

Test / Examination	Visit name	Visit Label	Visit Number	Reference Start Date/Time	Relative Day Number
Informed consent/assent	Screening	Screening	1		
Randomization	Screening	Screening	1		
Demographic data	Screening	Screening	1		

Test / Examination	Visit name	Visit Label	Visit Number	Reference Start Date/Time	Relative Day Number
Medical history	Screening	Screening	1		
Physical examination	Screening	Screening	1		
In-or outpatient	Screening	Screening	1		
Stool frequency within the last 24 hours	Screening	Screening	1		
Inclusion/exclusion criteria	Screening	Screening	1		
Vitals signs	Screening	Screening	1		
Dispense study drug	Screening	Screening	1		
Concomitant medication	Screening	Screening	1		
Adverse events	Screening	Screening	1		
Dispense diary	Screening	Screening	1		
Collect diary	End of Treatment	End of Treatment	2	Date of last dose of study treatment	Day 6 (*)
Physical examination	End of Treatment	End of Treatment	2	Date of last dose of study treatment	Day 6 (*)
Compliance check	End of Treatment	End of Treatment	2	Date of last dose of study treatment	Day 6 (*)
Adverse events	End of Treatment	End of Treatment	2	Date of last dose of study treatment	Day 6 (*)
Collect study drug	End of Treatment	End of Treatment	2	Date of last dose of study treatment	Day 6 (*)

25

Test / Examination	Visit name	Visit Label	Visit Number	Reference Start Date/Time	Relative Day Number
Concomitant medication	End of Treatment	End of Treatment	2	Date of last dose of study treatment	Day 6 (*)
Adverse events	Follow- Up	Safety follow- up (phone call 5-7 days after Visit 2)	3	Investigator 's phone call 5-7 days after end of treatment visit	Day 11-13
Concomitant medication	Follow- Up	Safety follow- up (phone call 5-7 days after Visit 2)	3	Investigator 's phone call 5-7 days after end of treatment visit	Day 11-13

(*) or within 24 h after recovery if this occurs before day 6

6.2 Further Specifications to the Standard Tables in Module 2

Not applicable.

6.3 Other Further Specifications

Not applicable.

7. CHANGES TO PLANNED ANALYSES

No changes will be made to the final SAP

8. **REFERENCE**

- 1. Abbott SAP Module 2
- 2. CDISC terminology, see http://www.cdisc.org.

9. **APPENDICES**

9.1 Study Flowchart

Note: Any additional medical procedures not included into this study protocol can be performed within routine clinical practice in each medical institution.

Period	Screening	End of Treatment period	Safety follow-up (phone call 5-7 days after Visit 2)
Visit	1	2	3
Day	1	6 ²	11-13
Informed consent	Х		
Randomization	Х		
Demographic data	Х		
Medical history	Х		
Pregnancy Test ⁴	Х		
Physical examination ³	Х	Х	
In- or outpatient	Х		
Stool frequency within the last 24 hours	Х		
Inclusion/exclusion criteria	Х		
Vitals signs	Х	Х	
Dispense study drug	Х		
Concomitant medication	Х	Х	X if applicable
Compliance check		Х	
Adverse events	Х	Х	X
Collect study drug		X	
Dispense diary	X ¹		
Collect diary		X	

¹ Subjects' parent/caregivers have to fill in their daily diaries continuously.

² or within 24 h after recovery if this occurs before day 6

³ including assessment of dehydration level

⁴ for females of child-bearing potential, urine test

9.2 Tables, Listings and Figures

9.2.1 Tables

For the shells of the non-standard tables, see Section 10.1.

				Produced	for:	
Output Code	Clinical Domain	Output Number	Title	Headline Results	SMT	Interim Analysis
DST001	Subject Disposition	10.1.1.1	Subject Disposition - All Subjects Allocated to Treatment Subject Sample			
DVT001	Protocol Deviations	10.1.1.2	Protocol Deviations – All Subjects Allocated to Treatment Subject Sample			
DVT002	Protocol Deviations	10.1.1.3	Subject Samples - All Subjects Allocated to Treatment Subject Sample			
DMT002	Demographic Data	10.1.1.5	Demographics – Safety Sample			
DMT002	Demographic Data	10.1.1.6	Demographics –Full Analysis Subject Sample			
VST003	Vital Signs	10.1.1.8	Other Baseline Characteristics – Safety Sample			
VST003	Vital Signs	10.1.1.9	Other Baseline Characteristics – Full Analysis Subject Sample			
MHT001	Medical History	10.1.1.10	Medical History – All Subjects Allocated to Treatment Subject Sample			
MHT001	Medical History	10.1.1.11	Medical History – Safety Sample			
MHT001	Medical History	10.1.1.12	Medical History – Full Analysis Subject Sample			
NST001	Medical History	10.1.1.13	Main Diagnosis - All Subjects Allocated to Treatment Subject Sample			
NST002	Medical History	10.1.1.14	Main Diagnosis - Safety Sample			
NST003	Medical History	10.1.1.15	Main Diagnosis - Full Analysis Subject Sample			
CMT001	Concomitant Medications	10.1.1.16	Concomitant Medications – All Subjects Allocated to Treatment Subject Sample			
CMT001	Concomitant Medications	10.1.1.17	Concomitant Medications – Safety Sample			

30

				Produced	for:	
Output Code	Clinical Domain	Output Number	Title	Headline Results	SMT	Interim Analysis
CMT001	Concomitant Medications	10.1.1.18	Concomitant Medications – Full Analysis Subject Sample			
DAT001	Treatment Compliance	10.1.1.19	Compliance to Study Drug – All Subjects Allocated to Treatment Subject Sample			
DAT001	Treatment Compliance	10.1.1.20	Compliance to Study Drug – Safety Sample			
DAT001	Treatment Compliance	10.1.1.21	Compliance to Study Drug – Full Analysis Subject Sample			
AET001	Adverse Events	10.1.3.1.1	Overall Summary of Adverse Events – Safety Sample			
AET002	Adverse Events	10.1.3.1.2	Incidence of TEAEs – Safety Sample			
AET005	Adverse Events	10.1.3.1.3	Incidence of TEAEs With a Reasonable Possibility for a Causal Relationship (Investigator's Judgment) – Safety Sample			
AET006	Adverse Events	10.1.3.1.4	Incidence of TEAEs by Maximum Severity (Investigator's Judgment) – Safety Sample			
AET007	Adverse Events	10.1.3.1.5	Incidence of TESAEs – Safety Sample			
AET008	Adverse Events	10.1.3.1.6	Incidence of TEAEs Leading to Study Termination – Safety Sample			
VST001	Vital Signs	10.1.3.2.1	Summary of Vital Signs – Safety Sample			
VST002	Vital Signs	10.1.3.2.2	Incidence of Markedly Abnormal Vital Signs – Safety Sample			
NST004	Physical Examination	10.1.3.3.1	Physical Examination by subgroup (Toilet trained / Not toilet trained) – Safety Sample			
NST005	Exposure	10.1.3.4.1	Treatment duration – Safety Sample			
NST006	Exposure	10.1.3.4.2	Cumulative dose by weight (mg/kg) – Safety Sample			

				Produced	for:	
Output Code	Clinical Domain	Output Number	Title	Headline Results	SMT	Interim Analysis
NST007	Subject Status	10.1.4.1.1	Duration of diarrhea: time to last diarrheal/watery stool before recovery by days. Kaplan-Meier analysis – Full Analysis Subject Sample			
NST008	Subject Status	10.1.4.1.2.1	Duration of diarrhea. Descriptive statistics (in hours) and comparison results – Full Analysis Subject Sample			
NST009	Subject Status	10.1.4.1.2.2	Duration of diarrhea. Cox Regression Model – Full Analysis Subject Sample			
NST010	Subject Status	10.1.4.1.3.1	Duration of diarrhea. Descriptive statistics (in hours) and comparison results for age group from 3 to < 24 month – Full Analysis Subject Sample			
NST011	Subject Status	10.1.4.1.3.2	Duration of diarrhea. Descriptive statistics (in hours) and comparison results for age group from >= 2 to <12 years – Full Analysis Subject Sample			
NST012	Subject Status	10.1.4.1.3.3	Duration of diarrhea. Descriptive statistics (in hours) and comparison results for age group from 12 to < 18 years – Full Analysis Subject Sample			
NST013	Subject Status	10.1.4.1.3.4	Duration of diarrhea. Descriptive statistics (in hours) and comparison results for weight/dosing category infants less than 9 kg – Full Analysis Subject Sample			
NST014	Subject Status	10.1.4.1.3.5	Duration of diarrhea. Descriptive statistics (in hours) and comparison results for weight/dosing category infants from 9 kg to < 13 kg – Full Analysis Subject Sample			

				Produced	for:	
Output Code	Clinical Domain	Output Number	Title	Headline Results	SMT	Interim Analysis
NST015	Subject Status	10.1.4.1.3.6	Duration of diarrhea. Descriptive statistics (in hours) and comparison results for weight/dosing category children from 13 kg to 27 kg – Full Analysis Subject Sample			
NST016	Subject Status	10.1.4.1.3.7	Duration of diarrhea. Descriptive statistics (in hours) and comparison results for weight/dosing category children from more than 27 kg to 60 kg – Full Analysis Subject Sample			
NST017	Subject Status	10.1.4.1.3.8	Duration of diarrhea. Descriptive statistics (in hours) and comparison results for weight/dosing category children or adolescents of 60 kg or higher – Full Analysis Subject Sample			
NST018	Subject Status	10.1.4.1.3.9	Duration of diarrhea. Number of stools during the study - Full Analysis Subject Sample			
NST019	Subject Status	10.1.4.1.4	Duration of diarrhea: time to last diarrheal/watery stool before recovery by days. Kaplan-Meier analysis – Per Protocol Subject Sample			
NST020	Subject Status	10.1.4.1.5.1	Duration of diarrhea. Descriptive statistics (in hours) and comparison results – Per Protocol Subject Sample			
NST021	Subject Status	10.1.4.1.5.2	Duration of diarrhea. Cox Regression Model – Per Protocol Subject Sample			
NST022	Subject Status	10.1.4.1.6.1	Duration of diarrhea. Descriptive statistics (in hours) and comparison results for age group from 3 to < 24 month – Per Protocol Subject Sample			

				Produced	for:	
Output Code	Clinical Domain	Output Number	Title	Headline Results	SMT	Interim Analysis
NST023	Subject Status	10.1.4.1.6.2	Duration of diarrhea. Descriptive statistics (in hours) and comparison results for age group from >= 2 to <12 years – Per Protocol Subject Sample			
NST024	Subject Status	10.1.4.1.6.3	Duration of diarrhea. Descriptive statistics (in hours) and comparison results for age group from 12 to < 18 years – Per Protocol Subject Sample			
NST025	Subject Status	10.1.4.1.6.4	Duration of diarrhea. Descriptive statistics (in hours) and comparison results for weight/dosing category infants less than 9 kg – Per Protocol Subject Sample			
NST026	Subject Status	10.1.4.1.6.5	Duration of diarrhea. Descriptive statistics (in hours) and comparison results for weight/dosing category infants from 9 kg to < 13 kg – Per Protocol Subject Sample			
NST027	Subject Status	10.1.4.1.6.6	Duration of diarrhea. Descriptive statistics (in hours) and comparison results for weight/dosing category children from 13 kg to 27 kg – Per Protocol Subject Sample			
NST028	Subject Status	10.1.4.1.6.7	Duration of diarrhea. Descriptive statistics (in hours) and comparison results for weight/dosing category children from more than 27 kg to 60 kg – Per Protocol Subject Sample			
NST029	Subject Status	10.1.4.1.6.8	Duration of diarrhea. Descriptive statistics (in hours) and comparison results for weight/dosing category children or adolescents of 60 kg or higher – Per Protocol Subject Sample			

				Produced	for:	
Output Code	Clinical Domain	Output Number	Title	Headline Results	SMT	Interim Analysis
NST030	Subject Status	10.1.4.1.6.9	Duration of diarrhea. Number of stools during the study - Per Protocol Subject Sample			
NST031	Subject Status	10.1.4.1.7	Number of stools per day (toilet trained subgroup) – Full Analysis Subject Sample			
NST032	Subject Status	10.1.4.1.8	Number of watery stools per day (toilet trained subgroup) – Full Analysis Subject Sample			
NST033	Subject Status	10.1.4.1.9	Cumulative number of stools until recovery or end of treatment by days – Full Analysis Subject Sample			
NST034	Subject Status	10.1.4.2.1	Time to recovery: time to evacuation of the first of two consecutive normal stools or no stool after first normal stool within 12 hours by days. Kaplan-Meier analysis – Full Analysis Subject Sample			
NST035	Subject Status	10.1.4.2.2.1	Time to recovery. Descriptive statistics (in hours) and comparison results – Full Analysis Subject Sample			
NST036	Subject Status	10.1.4.2.2.2	Time to recovery. Descriptive statistics (in hours) and comparison results – Full Analysis Subject Sample			
NST037	Subject Status	10.1.4.2.2.3	Time to recovery. Descriptive statistics (in hours) and comparison results for age group from 3 to < 24 month – Full Analysis Subject Sample			
NST038	Subject Status	10.1.4.2.2.4	Time to recovery. Descriptive statistics (in hours) and comparison results for age group from >= 2 to <12 years – Full Analysis Subject Sample			
NST039	Subject Status	10.1.4.2.2.5	Time to recovery. Descriptive statistics (in hours) and comparison results for age group from 12 to < 18 years – Full Analysis Subject Sample			

				Produced	for:	
Output Code	Clinical Domain	Output Number	Title	Headline Results	SMT	Interim Analysis
NST040	Subject Status	10.1.4.2.2.6	Time to recovery. Descriptive statistics (in hours) and comparison results for weight/dosing category Infants less than 9 kg – Full Analysis Subject Sample			
NST041	Subject Status	10.1.4.2.2.7	Time to recovery. Descriptive statistics (in hours) and comparison results for weight/dosing category Infants from 9 kg to < 13 kg – Full Analysis Subject Sample			
NST042	Subject Status	10.1.4.2.2.8	Time to recovery. Descriptive statistics (in hours) and comparison results for weight/dosing category Children from 13 kg to 27 kg – Full Analysis Subject Sample			
NST043	Subject Status	10.1.4.2.2.9	Time to recovery. Descriptive statistics (in hours) and comparison results for weight/dosing category Children from more than 27 kg to 60 kg – Full Analysis Subject Sample			
NST044	Subject Status	10.1.4.2.2.10	Time to recovery. Descriptive statistics (in hours) and comparison results for weight/dosing category Children or adolescents of 60 kg or higher – Full Analysis Subject Sample			
NST045	Questionnaires	10.1.4.2.3	Global Physician Assessment at the end of treatment – Full Analysis Subject Sample			
NST046	Questionnaires	10.1.4.2.4.1	Global Physician Assessment at the end of treatment for weight/dosing category Infants less than 9 kg – Full Analysis Subject Sample			

36

				Produced for:		
Output Code	Clinical Domain	Output Number	Title	Headline Results	SMT	Interim Analysis
NST047	Questionnaires	10.1.4.2.4.2	Global Physician Assessment at the end of treatment for weight/dosing category Infants from 9 kg to < 13 kg – Full Analysis Subject Sample			
NST048	Questionnaires	10.1.4.2.4.3	Global Physician Assessment at the end of treatment for weight/dosing category Children from 13 kg to 27 kg – Full Analysis Subject Sample			
NST049	Questionnaires	10.1.4.2.4.4	Global Physician Assessment at the end of treatment for weight/dosing category Children from more than 27 kg to 60 kg – Full Analysis Subject Sample			
NST050	Questionnaires	10.1.4.2.4.5	Global Physician Assessment at the end of treatment for weight/dosing category Children or adolescents of 60 kg or higher – Full Analysis Subject Sample			

